### ***Covariates***

#### ***Demographics***

- Age
- Race/ethnicity
- Gender
- BMI

- Co-morbidities
- Fracture classification
- Time until definitive fixation
- Tobacco use
- Workers compensation status
- Level of education
- Marital status
- Personal income
- Health insurance
- Working status before injury

These data will be abstracted from the medical record by the research staff.

*Additional Outcomes*

- Time until full weight bearing
- Time until return to work
- Compliance with weight bearing status
- Compliance with prescribed treatment

These data will be patient reported

*Complications*

- Nonunion
- Malunion
- Infection: Deep
- Infection: Superficial
- Osteomyelitis
- Wound breakdown
- Skin slough: partial thickness
- Skin slough: full thickness
- Additional surgeries: Strayer recession, Achilles lengthening, hardware removal, amputation, or arthrodesis.
- Rehospitalizations

These data will be captured during clinical exam at each office visit

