The results of the patients receiving Botox will be compared to those who received placebo. Average dorsiflexion will be determined and compared between the two groups as well as the percentage of patients who achieve 10 degrees or more of dorsiflexion. If applicable, the average dorsiflexion in the injured extremity will also be compared to the uninjured extremity to determine the average difference in dorsiflexion between the two groups. For statistical analysis, differences with a p value of <0.05 will be considered statistically significant.

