#### **D.4 Data Management**

All data will be entered into REDCap, a web-based data entry and management system that provides logic checks on input and checks for invalid entries. Data will be entered continuously as they are collected and stored in univariate form. We will also run standard checks for outliers, duplicates and other types of errors which may occur within a complex data file. All data files will be password protected and hard copies of blinded patient records will be maintained in locked cabinets in the research office.

*Data Analysis:* In order to determine that the randomization process produced comparable groups, we will use t-tests and cross-tabulations to compare patients in the treatment group to patients in the placebo group on the following variables: age, race, gender, BMI comorbidities, fracture classification, time until definitive fixation, tobacco use, workers compensation status, level of education, marital status, personal income, health insurance, working status before surgery, compliance with weight-bearing restrictions, compliance with prescribed treatment, time until full weight bearing and return to work.

Analyses will follow the intent-to-treat paradigm, under which all patients will be analyzed according to the treatment group to which they were randomized. Intention to treat analyses of outcomes will be conducted in two stages. First, we will conduct a bivariate analysis to examine relationships between assigned treatment

group, primary and secondary outcomes, and potential covariates and confounders (demographics, injury characteristics, co-morbidities). We will then use the results to build a multivariate model to predict primary and secondary outcomes based on treatment type.

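### Four post-injection outcomes are tested as if they were checks on randomisation, and neither the unadjusted comparison nor the data-built model is named as the primary analysis

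*Combined protocol and SAP*

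**What the plan says.** **Comparability check (D.4, Data Analysis).** The stated purpose is "In order to determine that the randomization process produced comparable groups". The tools are t-tests and cross-tabulations. Eighteen variables are listed. Fourteen are baseline or pre-injection items, from age to working status. The other four are "compliance with weight-bearing restrictions, compliance with prescribed treatment, time until full weight bearing and return to work".

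**The same four elsewhere.** D.2 puts them under its Additional Outcomes sub-heading, beginning with "Time until full weight bearing". D.3 has them noted at the 6- and 12-month visits.

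**Efficacy analysis (D.4).** "Intention to treat analyses of outcomes will be conducted in two stages". Stage one is bivariate and relates assigned group, primary and secondary outcomes, and a pool of demographic, injury and comorbidity variables. Stage two reads: "We will then use the results to build a multivariate model to predict primary and secondary outcomes based on treatment type". No entry rule, covariate list or limit on terms is given.

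**Unadjusted comparison (end of D.3).** "Average dorsiflexion will be determined and compared between the two groups", as will the percentage reaching 10 degrees, and "differences with a p value of <0.05 will be considered statistically significant". Neither this comparison nor the D.4 model is called primary.

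**The concern.** A comparability check can use only variables fixed before treatment. The four items are observed months after the injection, so a difference between arms could be chance, a treatment effect or an allocation fault, and the check cannot tell these apart. Section B.9 expects the injection to make rehabilitation more effective, so some downstream effect is at least conceivable. The two-stage outcome analysis covers primary and secondary outcomes only, and no other section names an outcome analysis for these four. A real difference would therefore be reported as a remark about randomisation.

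The second matter is which dorsiflexion result counts. With 10 patients per arm, a model whose covariates are chosen from the same data can differ from the unadjusted comparison in both estimate and p-value. D.5 and D.8 use the pilot to plan the full trial and allow its data to be pooled with it. D.5 also lets clearly inferior results end the programme. The choice of analysis therefore has consequences even though section A concedes that power is likely to be low.

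**Working it through.** **Plan's own figure.** The sample size of 20 (10 per arm) is given without effect size, SD, power or dropout, so there is no derivation to reproduce.

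**1. The four items.** Count in the D.4 list: 14 pre-injection + 4 post-injection = 18. Purpose in D.4: test randomisation. Status in D.2: outcome. Timing in D.3: 6 and 12 months, after injection. These cannot all stand together. The D.4 covariate pool does not include the four, so no adjustment for them is planned and they do not enter the dorsiflexion estimate.

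**2. Return to work, if a t-test on times is used.** D.4 does not say which test each variable gets. A patient not back at 12 months has no time to enter. Assumptions, none from the documents: exponential times, control median 6 to 12 months, hazard ratio 1.5 to 2.

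- Rate λ = ln 2 / median; horizon T = 12 months.
- Not returned by T: exp(−λT), which is 25% of controls at median 6 and 50% at median 12.
- Mean among returners: 1/λ − T·exp(−λT)/(1 − exp(−λT)).
- Restricted mean: (1 − exp(−λT))/λ.
- At median 9 and ratio 2, the difference among returners is 0.84 months and the restricted-mean difference is 2.36 months: 0.84/2.36 = 0.36.
- Over the whole range the returners-only comparison shows 28% to 46% of the restricted-mean difference.

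Time to full weight bearing is less exposed, because D.3 schedules it at 10 to 12 weeks.

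**3. Data-built model against unadjusted comparison.** From the documents: 10 v 10 and the 0.05 threshold. Assumed: normal outcome with SD 1; 6 or 14 candidate covariates, all unrelated to outcome, mutual correlation 0 or 0.3; entry at p<0.05, 0.10 or 0.20 on association with outcome, or with outcome or arm. There were 6,000 simulated trials per setting (Monte Carlo standard error 0.003 at 5%, 0.0065 at 50%).

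Unadjusted power at 1 SD: noncentral t, 18 df, noncentrality 1 × √(10/2) = 2.236, giving 56.2%.

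| True effect | Quantity | Data-built model | Unadjusted |
|---|---|---|---|
| 0 | Type I error | 4.6% to 5.6% | 5% |
| 0 | Either result may be cited | 5.7% to 8.8% | – |
| 0 | Mean residual variance / true | 0.75 to 0.94 | 0.99 to 1.01 |
| 1 SD | Mean estimate | 0.78 to 0.97 SD | 0.98 to 1.02 SD |
| 1 SD | Power | 37% to 54% | 56% |
| 1 SD | The two disagree on p<0.05 | about 5% to 30% of trials | – |

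The estimate shrinks because, when the effect is real, a noise covariate that happens to differ between arms is also correlated with the outcome. It is then more likely to enter and absorb part of the effect. The large losses come from 14 candidates at p<0.20. With 6 candidates at p<0.05 the estimate averages 0.94 to 0.97 SD with about 52% power.

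**4. Time point and method.** Section A tests at 6 and 12 months, and D.2 measures by goniometer and radiograph: 2 × 2 = 4 tests. If independent, the chance of at least one false positive is 1 − 0.95⁴ = 18.5%. Simulated at assumed correlations of 0.5 and 0.8 it is about 16% and 12%. Naming an analysis without naming these would leave the larger ambiguity open.

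**5. Precision of the pilot SD.** With 20 independent completers there are 18 df. The 95% limits are √(18/31.53) = 0.76 and √(18/8.23) = 1.48 times the estimate.

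**The case against.** **The first part changes no efficacy result.** This stands. The arms are still compared on the four items, D.4 attaches no action to a significant difference, and the opening of the comparison paragraph in D.3, which says in general terms that the arms will be compared, could be read to include them. What remains is a misclassification that affects how a difference would be interpreted.

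**The protocol does not expect a gait effect.** A reader might infer one from E.6.a.2, which mentions gait disturbance. That section goes on to say that pilon fractures were chosen because the non-weight-bearing period lets the toxin wear off before normal function resumes. It cannot be cited as expecting an effect on these items. The argument needs only that they follow treatment.

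**The return-to-work figures assume a test that D.4 does not assign.** Correct. A cross-tabulation of returned or not returned is equally open, and would be sound as an outcome analysis.

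**The model figures assume an entry rule that D.4 does not state.** Also correct. At the mild end the power loss matches that of two fixed noise covariates (50% to 52%). A reader might infer that such model building inflates false positives. Under one fixed rule it does not; only the freedom to cite either result adds a few points.

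**D.4 may be read as an ordered sequence,** with stage one matching the D.3 comparison and stage two adjusting it. That is a fair reading, but an order of steps does not say which result decides.

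**Conclusion.** Both faults lie in what the plan states, and both are worth correcting. The four items cannot test randomisation and should be reported as outcomes. This rests on the documents alone, and the consequence is one of interpretation, not bias in the primary estimate.

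The absence of a named primary analysis also rests on the documents alone. Its size is conditional. Under assumed p-value entry the cost at a true 1 SD effect runs from slight (0.94 to 0.97 SD, about 52% power) to substantial (0.78 SD; at worst 37% power), against an unbiased estimate and 56%.

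A reader might go further and infer that the full trial will be underpowered because the model's residual variance is too small. The documents do not say which SD the power analysis will use, so that does not follow; it is a reason to name the SD now.

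**What to change.** 1. **Comparability check.** Remove the four items from the D.4 list and report them by arm as outcomes with 95% confidence intervals. For the two times, use proportions at 6 and 12 months or Kaplan-Meier estimates censored at last visit. Limit return to work to patients working before injury.
2. **Primary analysis.** Name the unadjusted between-arm difference in mean dorsiflexion, at one time point and by one measurement method, both chosen before unblinding. The other time point, the other method and the 10-degree percentage become secondary.
3. **Adjusted analysis.** Replace the data-built model with one supportive model using one or two baseline covariates fixed before unblinding, each as a single term (for example age, and fracture classification in two levels).
4. **Full-trial planning.** Base the power analysis on the unadjusted within-arm SD with its 95% interval: 0.76 to 1.48 times the estimate with 20 independent completers, wider with loss to follow-up or with bilateral cases, whose legs D.3 randomises separately.

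**Cost.** Wording only; no new data. Two fixed covariates use two of the 18 residual df. At 1 SD, power is about 50% to 52% if both are noise and 57% to 59% if one correlates 0.4 with outcome, against 56% unadjusted, so that model should stay supportive. Return to work will be descriptive: if 70% were working (7 per arm, assumed), 6/7 v 4/7 is a difference of 29 points with a 95% interval of −17 to 63.

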#### **D.5 Pilot Data**

Currently, no previous work has been done on this project and therefore no pilot data is available. If funding for the entire study is unable to be secured, partial funding will be used for the procurement of pilot data. A pilot study will consist of 20 patients, 10 randomized to each group, and will be executed in the same manner as the full trial. A pilot study will show that the investigators and research staff are capable of implementing this prospective, double-blind, placebo controlled trial which will serve to strengthen further external grant proposals. At the conclusion of the pilot study, blinding will be broken and the data will be analyzed. Those data will be used to support or modify the power analysis for the full study and will eventually be incorporated into the full study cohort. If clearly inferior results are observed in the intervention group, those data will be published and the full trial will not be conducted.

#### **D.6 Estimated Timeline**

Due to the large number of trauma patients treated at our institution, a retrospective review of the number of cases indicates an incidence of 108 tibial plafond fractures treated per year. With an expected enrollment rate of 60% and a goal sample size of 20 patients, we expect enrollment to take 4 months, making this study quite feasible.

	Year 1				Year 2				Year 3			
	Q1	Q2	Q3	Q4	Q1	Q2	Q3	Q4	Q1	Q2	Q3	Q4
Train research staff on study procedures												
Train surgeons on dorsiflexion measuring device												
Patient Enrollment												
Patient Follow-up at 6 and 12 months												
Data Analysis												
Manuscript development, submission, and preparation of final report												

#### **D.7 Potential Problems**

In a busy trauma center, the enrollment of patients in prospective randomized study can be difficult. We will train the attendings, fellows, residents, and our research staff to identify potential candidates for the study. Information about the study including the inclusion/exclusion criteria will be readily available online or on study information cards provided to the staff and residents. Additionally, all surgical staff will receive an in-service training session so that they are aware of the study protocol to be followed in the operating room. There will be approximately 14 days between the time of injury and definitive fixation giving ample time for patient identification and obtaining informed consent.

#### **D.8 Future Directions**

At the conclusion of this pilot study, the data collected will be unblinded and analyzed. Those data will be used to aid in a power analysis to determine the sample size needed for a full trial. This protocol will then be amended to include the appropriate number of patients needed to be enrolled in order to have the appropriate

power. If no changes are made to the protocol, the data from this pilot will be combined with the data of the full study cohort.

## **E. Human Subjects**

### **E.1 IRB Statement**

As this study involves the inclusion of live human subjects and their personal information, we will strictly follow the guidelines and procedures outlined by our institutions IRB. Ensuring patient safety and maintaining patient confidentiality are of paramount importance and taken extremely seriously by the investigators of this study.

### **E.2 Study Population**

All subjects involved in this study will be ages 18 and older who have sustained a fracture of the tibial plafond. All patients will have their injury treated in a staged protocol, meaning primary external fixation followed by definitive fixation within 3 weeks of the injury.

#### Inclusion Criteria

- Patients 18 and older with a tibial plafond fracture to be treated by a staged protocol involving primary external fixation and definitive fixation within 3 weeks from the injury.
  - Non-definitive, interval procedures such as repeat irrigation and debridement and fibular fixation will be allowed

#### Exclusion Criteria

- Younger than 18 years of age.
- Significant traumatic brain injury or cognitive disability that would interfere with post-operative rehabilitation and study questionnaires.
- Nerve, vascular, or tendon injury of the lower leg: injury to the tibial or peroneal motor nerves, injury to the posterior tibial artery requiring repair, or laceration of tendons that are involved in plantar flexion or dorsiflexion of the ankle which require repair.
- History of prior lower extremity fracture to the tibia or ankle of the affected limb.
- Incarcerated patients.
- Patients unable or unwilling to return for follow-up examination.
- Pregnant or lactating patients.
- History of disease affecting the neuromuscular junction (ex: myasthenia gravis).
- Use of aminoglycoside antibiotics at the time of definitive fixation.
- Ipsilateral foot injury that will impair dorsiflexion exercises: Lisfranc injuries, fractures or dislocations of the talus, calcaneus, navicular, cuboid, cuneiforms, or metatarsals (phalanx fractures or dislocations will not be excluded).
- Patients receiving Botulinum Toxin A for other reasons.
- Patients with a known hypersensitivity to Botulinum toxin A.
- Gustilo Anderson type III B and C.
- Patients with a weight greater than 115 kg – to ensure proper injection locations.
- Patients taking non-depolarizing neuromuscular blocking agents (not including those used for general anesthesia).

### **E.3 Inclusion of Women and Minorities in Study**

The study population will be representative of the typical trauma population seen at Carolinas Medical Center – Main. Carolinas Hospital System is the largest provider in the region with a large catchment area encompassing western North Carolina and South Carolina. As the region's busiest trauma center, patients of all ages, genders, ethnicities, and backgrounds present to CMC, which is representative of the diverse population enjoyed by this region of the country. Women and minority groups will all be included in the study. Based on previous clinical series of patients at our institutions, we expect that 70% of our patients will be men and 25% minority patients.

#### **E.4 Description of the Screening Procedures and Recruitment Process**

Potential patients will be recruited during the index hospitalization or as a referral from an outside physician. Patients that may be eligible for the study will be evaluated by the attending physician to determine whether the inclusion and exclusion criteria are met. An attending surgeon will approach patient about volunteering for the research study, and if patient expresses interest, the formal education and consent process will be initiated by research staff. The research assistant or coordinator will then discuss the research and enrollment process and consent patients expressing willingness to participate.

#### **E.5 Description of the Informed Consent Process**

Once a patient has expressed interest in the study, a member of the treatment team will provide each patient with sufficient time and information to make a well-informed decision on whether or not to enroll in the study based on the risks and benefits imposed. There are strong ethical and practical reasons for striving for quality in the consent process and is taken seriously by all those involved in this study. Decisions made hastily or without accurate and adequate information are not in the patient's or the investigators' interest. Materials to inform prospective participants and to obtain consent will be developed in conjunction with the Steering Committee and consultants as required to ensure that they are accessible, informative and culturally sensitive.

Persons who meet the initial eligibility criteria for the study will be told of the trial, its purpose, and the general expectations of those enrolled. Those interested in further screening and willing to participate will be given a copy of the consent. Formal consent, as represented by the act of signing and dating an IRB approved consent statement for the trial, will occur after the final evaluation for eligibility and a review of what is involved in the trial. Persons will be reminded of the expectations placed on them if they enroll. They will be advised not to enroll if they are uncertain that they would be willing to accept treatment as assigned by a random process. Ambivalent subjects should not be enrolled. Persons will be given an opportunity to query study personnel on issues needing clarification. Patients who no longer wish to be involved in the study will be withdrawn immediately at their request and continue to receive the standard of care.

#### **E.6 Risk/Benefits Assessment**

**E.6.a Foreseeable Risks:** There are minimal risks inherent in this study. Both study arms will receive the current standard of care in the treatment of their tibial plafond fractures. The treatment group, however, will receive intramuscular injections of botulinum toxin A; an indication which is considered "off-label" as it is not an FDA approved indication of the product. Botox has been used safely and effectively for many years for similar "off-label" indications in the orthopaedic literature. Great care was taken to ensure that Botox is used safely and correctly in this study. All effects of Botox are completely reversible if given enough time, and it is felt that botulinum toxin injections will pose minimal risk to patients when used correctly.

##### **5.6.a.1 Botulinum Toxin Safety**

Botulinum Toxin A has been approved by the FDA for more than 20 years and has a long-established safety profile. When used correctly, the side effects of Botulinum Toxin type A injections are uncommon and usually mild and transient. Local side effects are the most common and are usually mild pain at the injection site and adjacent muscle weakness due to diffusion of the toxin across fascial barriers. Systemic side effects are very rare and include mild generalized weakness, urinary incontinence, constipation, and dysphagia; all of which are typically seen in susceptible individuals. Botox is contraindicated in patients with a history of neuromuscular disorder such as myasthenia gravis, and in patients receiving aminoglycoside antibiotics or non-depolarizing neuromuscular blocking agents, as these can all potentiate the effects of the toxin. It is also relatively contraindicated in patients with a history of pseudobulbar palsy and frequent chest infections for concern over aspiration pneumonia, an exceedingly rare, but serious side effect. These adverse events are not expected to cause problems based on our study design and patient population.

Of the local side effects, pain at the injection site is unlikely to be noticed by the patient as injections will be administered under general anesthesia and the patient's co-committent injury will likely dwarf any residual pain from the injection. The diffusion of Botox into adjacent muscle groups is not only inconsequential, but in-fact desired based on our study design. Although all injections will be made in the muscle belly of the gastrocnemius, diffusion into the deeper soleus muscle would provide additional weakness of the gastrosoleus complex and potentially result in better outcomes without causing additional functional impairment

In order to minimize the occurrence of systemic side effects, the amount of Botox utilized in this study will be well below the maximum safe dose for Botox, 12U/kg, even if bilateral pilon fractures are both randomized to the treatment group. In addition, patients with a history of a neuromuscular disorder, who are receiving aminoglycoside antibiotics or non-depolarizing neuromuscular blocking agents, or women who are or may become pregnant will be excluded from this trial. Patients reporting dysphagia or aspiration are typically those undergoing injections for cervical dystonia, and may be considered a local side effect rather than a systemic one. Based on the remote injection site utilized for this study, dysphagia and aspiration are unlikely to be experienced. The average total dose of 200U of Botulinum Toxin A will be injected into the gastrocnemius of the effected extremity and was chosen based on the effective dose for the average gastrocnemius from other studies.

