## **D. Research Design and Methods**

We will use a prospective double-blind randomized placebo-controlled study design. Subjects will be enrolled as inpatients or during the initial office visit by orthopaedic clinical research staff. After routine evaluation reveals that a patient meets the inclusion and exclusion criteria (below), informed consent will be obtained. Demographic data will be recorded. Patients will be block randomized by opaque, sealed-envelope to either a treatment group or a placebo group (N=20; N=10 treatment, N=10 placebo).

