#### Exclusion Criteria

- Younger than 18 years of age.
- Significant traumatic brain injury or cognitive disability that would interfere with post-operative rehabilitation and study questionnaires.
- Nerve, vascular, or tendon injury of the lower leg: injury to the tibial or peroneal motor nerves, injury to the posterior tibial artery requiring repair, or laceration of tendons that are involved in plantar flexion or dorsiflexion of the ankle which require repair.
- History of prior lower extremity fracture to the tibia or ankle of the affected limb.
- Incarcerated patients.
- Patients unable or unwilling to return for follow-up examination.
- Pregnant or lactating patients.
- History of disease affecting the neuromuscular junction (ex: myasthenia gravis).
- Use of aminoglycoside antibiotics at the time of definitive fixation.
- Ipsilateral foot injury that will impair dorsiflexion exercises: Lisfranc injuries, fractures or dislocations of the talus, calcaneus, navicular, cuboid, cuneiforms, or metatarsals (phalanx fractures or dislocations will not be excluded).
- Patients receiving Botulinum Toxin A for other reasons.
- Patients with a known hypersensitivity to Botulinum toxin A.
- Gustilo Anderson type III B and C.
- Patients with a weight greater than 115 kg – to ensure proper injection locations.

- Patients taking non-depolarizing neuromuscular blocking agents (not including those used for general anesthesia).

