### **D.3 Methods**

Orthopaedic surgery attendings and residents will identify potential study candidates during the initial consultation based on the presence of a tibial plafond fracture. If the patient meets the inclusion and exclusion criteria (noted above), a member of the treatment team will discuss the study with eligible patients. If the patient expresses interest in the study, the physician will notify the research staff. Orthopaedic Clinical Research staff will describe study procedures in detail and go through the informed consent process to enroll the patient in the study. Patients will be informed of the “off-label” usage of botulinum toxin injections as well as the potential side effects.

Once informed consent is obtained and the patient is enrolled in the study, the attending surgeon will classify the fracture based on the AO/OTA classification system (Figure 1). Study participants will then be block randomized and assigned by sequentially numbered sealed opaque envelopes to one of the two treatment groups based on computerized selection: those who receive intramuscular botulinum toxin injections at the time of definitive fixation, and those who receive placebo. Patients with bilateral pilon fractures and no other lower extremity injuries of the tibia, ankle, or foot that would further impair dorsiflexion stretching or other

rehabilitation exercises will have each extremity randomized and evaluated separately. Patients with a unilateral tibial plafond fracture and no injury of the contralateral tibia, ankle, or foot will be placed in a subgroup of patients who will have their unaffected extremity examined for comparison. Patients with an injury to the contralateral extremity that would exclude them from this subset will have only the extremity with the pilon fracture analyzed.

[figure not shown]

Figure 1.

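### The risk section excludes women who could become pregnant, but both eligibility lists that screeners apply exclude only pregnant or lactating patients

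*Combined protocol and SAP*

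**What the plan says.** Section 5.6.a.1 lists the exclusions meant to reduce systemic side effects. It names neuromuscular disorder, aminoglycoside antibiotics and non-depolarizing neuromuscular blockers, and it adds that "women who are or may become pregnant will be excluded from this trial".

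The exclusion criteria appear twice, in D.1 and in E.2. On this subject both have one identical line: "Pregnant or lactating patients".

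Eligibility is tied to those criteria in three places:
- Section D: "After routine evaluation reveals that a patient meets the inclusion and exclusion criteria (below), informed consent will be obtained".
- Section D.3, where discussion of the study with the patient is conditional: "If the patient meets the inclusion and exclusion criteria (noted above").
- Section E.4: possible candidates are "evaluated by the attending physician to determine whether the inclusion and exclusion criteria are met".

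Section D.7 adds that the criteria will be given to staff online or on information cards. Section E.3 says that "Women and minority groups will all be included in the study" and that "we expect that 70% of our patients will be men".

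**The concern.** The risk/benefit assessment describes a protection that the enrolment rules do not contain. Someone judging the trial's risks from section E.6 would conclude that women who could become pregnant will not be enrolled. Someone screening from the lists would enrol them. Both texts cannot be followed for the same patient.

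The product is used off-label (E.6.a), and the clause is presented as a safety measure, so the mismatch bears on patient protection as well as on tidiness. It also matters beyond the pilot. Section D.8 foresees amending this same protocol for a full trial and pooling the pilot data if nothing else changes, so an unresolved criterion could carry forward.

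**Working it through.** The plan gives no figure on this point to reproduce, so the main check is a comparison of texts.

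**Step 1. Is the difference one of substance?** The exclusions named in the 5.6.a.1 sentence compare with the lists as follows.

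| Exclusion in 5.6.a.1 | In D.1 list | In E.2 list |
|---|---|---|
| Neuromuscular disorder | Yes, in slightly different words | Yes, same line as D.1 |
| Aminoglycosides | Yes | Yes |
| Non-depolarizing blockers | Yes | Yes |
| Women who are pregnant | Yes | Yes |
| Women who could become pregnant | No | No |

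Only the last item has no counterpart. The phrase is undefined: it could mean any woman able to conceive, or a woman likely to conceive within some period. Under either meaning it is wider than pregnant or lactating.

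**Step 2. Does other text close the gap?** No available section has a criterion on ability to conceive, intention to conceive, contraception or a pregnancy test. The screening text in D, D.3, D.7 and E.4 refers to the criteria and never sends staff to the risk section.

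**Step 3. How many patients could this concern?** Inputs: 20 patients (A, D) and 70% men (E.3).
- Expected women: 20 × (1 − 0.70) = 6.
- The share who could become pregnant is not given. Over a share of 0 to 1, the expected number affected is 0 to 6.
- Six is an expected count. More or fewer women could enrol.

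**Step 4. What would applying the exclusion cost in enrolment time?** Inputs from D.6: 108 fractures a year, 60% enrolled, target 20.
- The plan's own pace: 108 × 0.60 / 12 = 5.4 patients a month, and 20 / 5.4 = 3.7 months. The plan states 4, which agrees after rounding.
- Half of the women excluded (illustrative): 5.4 × (1 − 0.15) = 4.59 a month, and 20 / 4.59 = 4.4 months.
- All women excluded (the extreme): 5.4 × 0.70 = 3.78 a month, and 20 / 3.78 = 5.3 months.
- Largest delay: 5.3 − 3.7 = 1.6 months against the computed baseline, or 5.3 − 4 = 1.3 months against the rounded planned figure.

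**The case against.** The strongest reply is that there is little real ambiguity. The two lists agree with each other and are the operative rules, while 5.6.a.1 is narrative in a risk discussion and probably describes the criteria too broadly. On that view one phrase needs correcting and no new restriction is called for. Part of this stands: the documents do point staff to the lists, and they do not show which text was intended. But that is also why the safeguard would go unapplied, and a safety statement that the trial does not honour has to be corrected one way or the other.

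Some stronger readings are tempting and are not supported:

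- **That the trial has no pregnancy precautions in practice.** Consent pages were removed from the review copy and may cover testing or contraception. Such wording would not reconcile 5.6.a.1 with the lists, but its absence cannot be inferred.
- **That the documents establish a hazard from conceiving after injection, with a four-month window.** E.6.a.2 gives an average of 2 to 4 months for local paralysis to improve. That is neither an upper limit nor a statement about pregnancy.
- **That six women is a ceiling, or that a particular number would receive the toxin.** Six is an expectation, and any split by arm would require assuming that every woman is affected.
- **That E.3 decides the matter.** It is a statement about representation. It sits alongside the exclusion of pregnant women without overriding it, so it cannot settle the wider clause either.

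**Conclusion.** The point holds as a contradiction between two stated rules. Section 5.6.a.1 claims an exclusion of women who could become pregnant, neither eligibility list contains it, and screening runs on the lists. Followed as written, the lists leave that safeguard unapplied.

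The scale is small and partly unknown: about 6 of 20 patients are expected to be women, and an unstated share of them fall in the gap. The enrolment figures assume that the 70% applies to the patients who would enrol, and that neither it nor the 60% rate already allows for this exclusion. No estimate, test or sample size depends on the point. It should be settled before enrolment opens, because it bears on patient safety and is cheap to correct.

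**What to change.** Choose one rule and state it identically in D.1, E.2 and 5.6.a.1.

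- **If the exclusion is intended:** replace the pregnancy line in both lists with something staff can apply, for example: *Patients who are pregnant or lactating, and women able to conceive who plan a pregnancy or are not using contraception during a stated period after injection.* The clinicians should set the period. Use the same wording in 5.6.a.1. Simply copying the current 5.6.a.1 phrase would leave screeners with an undefined test. A test based on plans and contraception also keeps more women eligible than one based on ability to conceive alone, which sits better with E.3.
- **If it is not intended:** narrow 5.6.a.1 to pregnant or lactating patients, so that the risk section no longer claims a protection the trial lacks.

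The first option costs one line in each list, one phrase in 5.6.a.1, and a screening question to support the new line. Somewhat fewer women would be eligible and enrolment would be slightly slower, within the bounds computed above. The second option costs one phrase. Neither changes sample size, visits or analysis.
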